9.2 Population Sets

9.2.1 Screened Analysis Set

The Screened Analysis Set (SCR) will consist of all subjects who sign an ICF. This analysis set will be used to report disposition and screening failures.

9.2.2 Enrolled Analysis Set

The **Enrolled Analysis Set (EAS)** will consist of all subjects who sign an ICF and enter the trial (and only subjects who meet all the inclusion criteria and none of the exclusion criteria).

CCI

Page 8 of 20

Strictly Confidential. © 2023, PRA Health Sciences. All rights reserved.

9.2.3 Full Analysis Set

The **Full Analysis Set (FAS)** comprises all the detections of the wearable sensors done on the subjects who took at least 1 dose of MITs (Cohort 1) or Abilify MyCite (Cohort 2), excluding those detections with device malfunction (invalid session and impedance is bad).

For the primary endpoint in Cohort 1, the **FAS-Cohort 1** is a subset of the FAS and consists all the detections for subjects who took at least 1 dose of MITs (Cohort 1).

For the primary endpoint in Cohort 2, the **FAS-Cohort 2** is a subset of the FAS and consists all the detections for subjects who took at least 1 dose of Abilify MyCite (Cohort 2).

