8.10 Other Assessments

8.10.1 Positive Detection Accuracy

The number of total DOIs will be reported by the site on the eCRF. Positive detections will be downloaded from the trial mobile device(s) for analysis.

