9.2 Datasets for Analysis

The following analysis samples are defined for this trial:

- Enrolled Sample: all subjects who sign an ICF and enter the trial (and only subjects who meet all the inclusion criteria and none of the exclusion criteria).
- The intent-to-treat (ITT) population: ITT population consists of all subjects who took at least 1 dose of MITs or Abilify MyCite.
- Safety Sample: all subjects who wear any patch or take any tablet from the trial and have any safety assessment.

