9.3 Handling of Missing Data for Primary and Secondary Endpoint Analysis

Missing data on PDA and/or detection latency measures will not be imputed.

9.4 **Statistical Analyses**

9.4.1 **Primary Endpoints**

The number of positive detections and PDA will be summarized for the D-Tect Patch for Cohort 1; the 95% CI of PDA will be provided using the Clopper-Pearson method. PDA is defined as PDA = $k \div n$, where n is the number of the total DOIs, and k is the number of positive detections by the patch.

For detection latency, summary statistics will be provided for Patch Detection Latency, Ingestion Data Transfer Latency, and Total Detection Latency. Kaplan-Meier curves will be plotted for all of the latency times.

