6.1 Changes from Protocol

There are no major discrepancies between protocol and SAP, only the following minor differences are described:

- 1. Population definitions (SCR, FAS, FAS-Cohort 1, and FAS-Cohort 2) added, the protocol specified the intent-to-treat population, however, the full analysis set will be used.
- 2. The unanticipated adverse device effects stated in the protocol removed from the analysis.
- 3. AEs leading to discontinuation of the investigational device removed from analysis, instead AEs leading to study discontinuation will be analyzed.

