10.6 Definition of Positive Detection Accuracy

The Positive Detection Accuracy (PDA) is defined as PDA = k/n, where *n* is the number of the total DOIs in FAS-Cohort 1 (malfunction sessions have been excluded from FAS-Cohort 1), and k is the number of total positive detections by the patch.

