12.5.1 Positive Detection Accuracy

For **FAS-Cohort 1**, the number of positive detections, the positive detection accuracy (PDA) and 95% Clopper-Pearson confidence interval (CI) will be summarized, for overall DOIs only.

Positive detections will not be reported in CRF and will rather be downloaded from the trial mobile device(s). All positive detections data will be listed together with directly observed ingestion data (Section 12.3.1) based on FAS-Cohort 1.

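### The SAP drops malfunction-session ingestions from the PDA denominator, the protocol's formula does not, and no all-ingestion PDA is planned; near the 95% limit one excluded miss can decide the result

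*SAP*

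**What the plan says.** **Protocol.** Section 9.4.1 defines PDA as k/n, "where n is the number of the total DOIs, and k is the number of positive detections by the patch". Section 8.10.1 gives the source of n: "The number of total DOIs will be reported by the site on the eCRF". Section 9.2 states that the "ITT population consists of all subjects who took at least 1 dose of MITs or Abilify MyCite"; it has no exclusion at session or ingestion level. Section 9.3 adds: "Missing data on PDA and/or detection latency measures will not be imputed".

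**SAP.** Section 9.2.3 defines the full analysis set (FAS) in terms of detections, "excluding those detections with device malfunction (invalid session and impedance is bad"). Section 10.6 applies this to PDA: n is the DOI total in FAS-Cohort 1, and "malfunction sessions have been excluded from FAS-Cohort 1), and k is the number of total positive detections by the patch". Section 12.5.1 plans PDA and its Clopper-Pearson interval for FAS-Cohort 1 only. Its reference to overall DOIs therefore means the DOIs left in that set.

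**What is declared.** SAP 6.1 says there are no major discrepancies with the protocol and lists, as a minor difference, that "the protocol specified the intent-to-treat population, however, the full analysis set will be used". It does not mention removed ingestions or a changed PDA denominator.

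**Listing.** SAP 12.5.1 says: "All positive detections data will be listed together with directly observed ingestion data (Section 12.3.1) based on FAS-Cohort 1". SAP 12.3.1 includes separate flags for detection, patch impedance and session validity.

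**Criterion.** Both documents (Protocol Table 3-1, SAP 9.1) state the primary PDA endpoint as a lower confidence limit above 95% while the patch is worn.

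**The concern.** The two documents define different primary quantities. The protocol's formula asks what share of all observed ingestions the system registered. The SAP asks what share it registered among ingestions not set aside for malfunction.

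The exclusion is unlikely to be neutral where it rests on impedance. Protocol 2 says an ingested marker can be detected only while the patch adheres to the skin. Protocol 8 makes a missing tablet registration the prompt for ruling out bad impedance. DOIs with bad impedance are therefore likely to contain more misses than the rest, and removing them would tend to raise PDA. For invalid sessions the documents give no basis for a direction.

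The SAP neither states nor references an impedance cut-off or a definition of a valid session. It also leaves some doubt whether both conditions are required or either is enough.

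At stake is whether a reader can tell if the 95% criterion was met on all observed ingestions. No planned summary gives that figure, the number of DOIs removed, or how many of those were missed. The listing may or may not show them: it carries the relevant flags but is labelled FAS-Cohort 1, the set from which malfunctions have been removed.

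**Working it through.** **Inputs.** Planned n = 24 × 15 = 360 DOIs, and assumed PDA 97.3% (Protocol 9.1, SAP 8.1). The interval is the two-sided 95% Clopper-Pearson interval (Protocol 9.4.1, SAP 12.5.1). The criterion is a lower limit above 95%. The documents give no malfunction rate.

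**Formula.** The lower limit for k detections in n DOIs is the 2.5% quantile of a Beta(k, n − k + 1) distribution.

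**1. The plan's own figure.** With k = 0.973 × 360 = 350.28 (not a whole number), the lower limit is 95.05%. The statement that 360 ingestions put the lower bound at 95% is reproduced, as a statement about precision. The expected number of misses is 360 × 0.027 = 9.7, so the planning assumption sits almost on the boundary.

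**2. Boundary on all DOIs.**
- 9 misses: 351/360 = 97.50%, lower limit 95.31%, met.
- 10 misses: 350/360 = 97.22%, lower limit 94.95%, not met.

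At n = 360 at most 9 misses are allowed.

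**3. Effect of excluding misses.** An excluded miss lowers n by one and leaves k unchanged.

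| Misses among 360 | All DOIs: lower limit | Misses excluded | After exclusion: lower limit |
|---|---|---|---|
| 10 | 350/360: 94.95%, not met | 1 | 350/359: 95.29%, met |
| 11 | 349/360: 94.60%, not met | 2 | 349/358: 95.28%, met |
| 12 | 348/360: 94.25%, not met | 3 | 348/357: 95.27%, met |

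**4. How likely is a result in that zone?** Take misses as Binomial(360, 0.027), with independent DOIs. P(exactly 10) = 12.6%, the outcome that one excluded miss reverses. P(10 to 12) = 32.8%, the outcomes that one to three excluded misses reverse. These are chances of landing in the reversible zone. They are not chances that a reversal occurs, which would also need the unknown number of excluded misses.

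**5. Exclusion unrelated to detection.** The chance of meeting the criterion at 97.3% is P(Binomial(n, 0.027) ≤ 9): 49% at n = 360, 51% at n = 355 and 55% at n = 345. The effect is then small.

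**6. Can exclusion work the other way?** The allowance is 9 misses at every n from 338 to 363, and 10 at n = 364. With 10 misses, 354/364 has a lower limit of 95.006% (met). Excluding one detected DOI gives 353/363 with 94.992% (not met). So if n exceeds 363, excluding detected DOIs can turn met into not met. This matters because 360 is a minimum, and Protocol 8 allows extra enrolment to replace missing ingestions.

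**The case against.** **The exclusion has a plausible basis.** The endpoint is conditional on the patch being worn, Protocol 2 uses impedance as the measure of skin contact, and detection requires adhesion. Leaving out poor-contact sessions could be a fair way to apply that condition. This stands as a possible reason, but neither document gives it as the reason. It is why the malfunction-excluded PDA should be kept, and why the choice of deciding figure belongs to the sponsor.

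**It is pre-specified.** SAP 9.2.3 and 10.6 state the exclusion openly, and SAP 6.1 names the FAS. This stands. The gap in 6.1 is limited to the exclusion and its effect on the denominator, and the documents give no support for reading it as concealment.

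**The listing may show the excluded DOIs.** Impedance and validity flags would serve little purpose if every malfunction were absent. The listing is ambiguous for this reason, and it cannot be said that the all-DOI result is lost.

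**Criteria may exist elsewhere.** Protocol 6.2 points to an operations manual, and SAP 6.0 is to be read with the CRF. What can fairly be said is that the SAP neither states nor references the criteria. Its wording reads most naturally as requiring both conditions.

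**The size is conditional and the study is called exploratory.** Both are true (SAP 8.1, 9.0), and they limit the severity. The 95% criterion nevertheless remains the stated primary endpoint in both documents.

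**A stronger reading.** A reader might infer that the exclusion can only help the device. The documents do not support that: n may exceed 360, where a reversal in the other direction is possible (step 6), and the direction for invalid sessions is unknown.

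**Conclusion.** The discrepancy is real and should be fixed. The protocol's formula as written uses all DOIs, the SAP's does not, SAP 6.1 does not mention the change, and no all-DOI PDA or count of excluded misses is planned.

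The effect can be decisive near the boundary: at n = 360 with 10 misses, one excluded miss moves the lower limit from 94.95% to 95.29%. That miss count has a 12.6% chance under a PDA of 97.3% and independent DOIs. Independence is an assumption; poor contact may well cluster within a patch and subject.

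The actual effect may be nil, because it depends on at least one missed DOI being excluded and the documents do not say how often malfunctions occur. That impedance-based exclusion would raise PDA is a likely direction inferred from Protocol 2 and 8, not an established one. Nor do the documents settle that the all-DOI figure must decide the criterion: the formula points that way, while the condition that the patch is worn leaves room for the other. They need to be reconciled.

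**What to change.** 1. **SAP 10.6 and 12.5.1:** report PDA with its Clopper-Pearson interval on all Cohort 1 DOIs, the Protocol 9.4.1 definition, beside the malfunction-excluded PDA. In the all-DOI figure, count a DOI without a positive detection as not detected. This is not imputation, since n comes from the eCRF and k from the downloaded detections.
2. **Protocol and SAP:** before detection data are seen, agree which of the two figures decides the 95% criterion and whether DOIs that are later replaced stay in n.
3. **Counts:** report the number of DOIs excluded and how many of those were undetected.
4. **SAP 12.3.1:** base the listing on all Cohort 1 DOIs.
5. **SAP 9.2.3:** state or reference the malfunction criteria, including whether both conditions or either is needed.
6. **SAP 6.1:** declare the exclusion and the changed denominator.
7. **Separately:** Protocol 1.1 and 2.1 and SAP 8.0 describe PDA relative to total marker detections, a third denominator. Change this to total DOIs.

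**Cost.** One extra PDA row, a wider listing and some wording. The flags are already planned, so no new data are needed. The all-DOI figure may be slightly less favourable and may include misses not caused by the patch, since Protocol 8 also names tablet contamination and subject anomalies.

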9.2.4 Safety Analysis Set

The **Safety Analysis Set (SAF)** will consist of all subjects who wear any patch or take any tablet from the trial and have any safety assessment.

| Analyses | SCR | EAS | FAS-Cohort 1 | FAS-Cohort 2 | SAF |
|--|--------------|--------------|--------------|--------------|--------------|
| Subject disposition | | \checkmark | | | |
| Demographic and baseline characteristics | | \checkmark | | | |
| Medical history | | \checkmark | | | |
| Prior and concomitant medications | | \checkmark | | | |
| Directly Observed Ingestion | | | \checkmark | \checkmark | |
| Study Drug Exposure | | | | \checkmark | |
| Patch Application and Removal | | | \checkmark | \checkmark | |
| Protocol deviation | | \checkmark | | | |
| Positive Detection Accuracy | | | \checkmark | | |
| Detection Latency Measures | | | \checkmark | \checkmark | |
| Adverse Events | \checkmark | | | | |
| Treatment-Emergent Adverse Events (TEAEs) | | | | | \checkmark |
| Deaths and Serious TEAEs | | | | | \checkmark |
| Vital Signs | | | | | \checkmark |

9.2.5 Summary of Analysis Sets

Abbreviations:

SCR = Screened Analysis Set,

EAS = Enrolled Analysis Set,

FAS = Full Analysis Set,

CCI

Page 9 of 20

Strictly Confidential. © 2023, PRA Health Sciences. All rights reserved.

SAF = Safety Analysis Set

10.0 Conventions and Derivations

10.1 Visit Windows

Table 2 shows study periods, visits, study days, and visit windows. The visit will be used for analysis according to the visit reported by the CRF.

Table 2: Study Visit Window

| Study Period | Study Visit | Study Day | Study Visit Window |
|-----------------------|-------------|-----------|--------------------|
| Eligibility screening | Visit 1 | -7 to 1 | - |
| Testing | Visit 2 | 1 | - |
| Follow-up | Visit 3 | 8 | + 2 days |

Study day will be calculated as

Study Day = Date of day - Date of Testing + 1

10.2 Unscheduled Visit Definition

An **Unscheduled Visit** is defined as any additional visit performed at the investigator's discretion, at any time between Testing (Day 1) and the Follow-Up Visit at Day 8.

10.3 Prior and Concomitant Medication

In this study, all medications and therapies taken by the subject from 7 days prior to D-Tect Patch application through the end of the evaluation period (defined as the time period during which subjects are evaluated for primary and/or secondary objectives) will be recorded.

A medication is considered to be prior if the start date and time is before the first ingestion date and time. A medication is considered to be concomitant if the medication is ongoing at, started together with, or started after the first ingestion date and time. Note that a medication can be considered both prior and concomitant.

10.4 Definition of Body Mass Index

The BMI (Body Mass Index) calculation divides a subject's weight in kilograms by their height in meters squared. The formula to calculate BMI is as follows:

BMI = weight (in kilograms) / (height (in meters))²

International System of Units for weight in kilogram (kg) and height in meter (m) will be used in analysis, the formulas for converting units of weight and height are as follows:

Weight in kilograms (kg) = Weight in pounds (lb) × 0.45359237

Height in meters (m) = Height in inches (in) $\times 0.0254$

CCI

Page 10 of 20

Strictly Confidential. © 2023, PRA Health Sciences. All rights reserved.

10.5 Definition of Treatment-Emergent Adverse Event

TEAEs are defined as AEs that occurred on or after the subject wears any patch or takes any tablet from the trial at test day, and the AEs that occurred before the subject wears any patch or takes any tablet and are worsening, serious, related, or resulted in death, discontinuation, or interruption of investigational product. All other AEs recorded in CRF are considered Non-Treatment-Emergent Adverse Events (Non-TEAEs).

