4.1 Type/Design of Trial

This two-cohort, open-label, prospective trial is designed to assess the PDA and detection latency of the D-Tect Patch.

Cohort 1

Cohort 1 will be completed in adult, healthy subjects. Subjects in Cohort 1 will take the MIT dose form. This trial will consist of up to 3 onsite visits including:

- Visit 1: Screening
- Visit 2 (Day 1): Testing, patch placement, DOI of MITs (conducted either on the same day as Visit 1 or up to 7 days after Visit 1)
- Visit 3 (Day 8): In-person safety follow-up and removal of patch (conducted approximately 7 days [+ 2 days] after applying the D-Tect Patch).

Cohort 2

Cohort 2 will be completed in adults with SMI who are prescribed and taking aripiprazole prior to trial entry. Subjects will take a single dose of Abilify MyCite at the same dose as subject's current aripiprazole prescription. Subjects will be instructed not to take their currently prescribed dose of aripiprazole at home on Day 1 of the trial when Abilify MyCite will be ingested. This trial will consist of up to 3 onsite visits including:

- Visit 1: Screening
- Visit 2 (Day 1): Testing, patch placement, DOI of a single dose of Abilify MyCite (conducted either on the same day as Visit 1 or up to 7 days after Visit 1)
- Visit 3 (Day 8): In-person safety follow-up and patch removal (approximately 7 days [+ 2 days] after applying the D-Tect Patch)

Cohorts 1 and 2

No trial procedures may be conducted prior to signing of the informed consent form (ICF), which will occur at Visit 1. Visit 2 involves patch application and DOI(s). Visits 1 and 2 may be combined and conducted on the same day. Subjects will return to the site on Day 8 (+ 2 days), 7 days following patch placement for a safety follow-up evaluation and to make final observations of patch wear (Visit 3). Any patches that remain on the subject will be removed at this visit. Any patch that falls off prior to the safety follow-up visit should be retained by the subject and given to trial staff at the scheduled follow-up visit.

A detailed schedule of events can be found in Table 1.3-1.

Confidential - Proprietary Information

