5.4 Screen Failures

A screen failure is a subject from whom informed consent is obtained and is documented in writing (ie, subject signs an ICF), but who does not have a patch applied. All AEs must be reported after subject informed consent has been obtained, including screen failures due to AEs, irrespective of trial intervention administration.

If the subject meets the definition of a screen failure in this trial, the following information will be recorded in the eCRF:

- Date of ICF signature •
- Visit date (screening visit) •
- Demographics •
- Result of eligibility assessment •
- Screen failure date •
- Reason for screen failure •
- Any AEs •

Individuals who do not meet the criteria for participation in this trial (screen failure) may not be rescreened.

Confidential - Proprietary Information

23

6 Trial Device(s) and Concomitant Therapy

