8.7.2 Eliciting and Reporting Adverse Events

The investigator will periodically assess subjects for the occurrence of AEs (serious and nonserious, associated with the use of the patch, MITs, and/or Abilify MyCite) from the time the ICF is signed until the end of the trial. For this trial, information on AEs will be followed until resolution as determined by the investigator. All patches will be removed by trial staff at the in-person follow-up visit. Any patch that peels off during the trial should be retained by the subject and given to trial staff at the scheduled in-person follow-up visit.

To avoid bias in eliciting AEs, subjects should be asked the nonleading question: "How have you felt since your last visit?" All AEs (serious and nonserious) must be collected. All SAEs must be reported within 24 hours of awareness, no later than 72 hours in the case of a weekend or holiday. If a patch-related AE is reported by the subject, it will be graded per Section 8.6.1. A full list of all reported events will be kept by the clinical research site.

For this trial, all IREs (SAEs) detected during the program must be reported to:

- [contact]
- (fax) [contact]

Reconciliation of AEs reported in this trial will be performed at the end of the trial.

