12.6.1 Treatment-Emergent Adverse Events

All AEs reported in the CRF will be coded using MedDRA.

An overall summary of TEAEs, including the number of events reported, and the number and percentage of subjects will be prepared by cohort in a table, as specified below:

- Subjects reporting at least 1 TEAE
- Subjects reporting at least 1 serious TEAE
- Subjects reporting at least 1 device/patch related TEAE
- Subjects reporting at least 1 device/patch related TEAE (by skin irritation score from 0-7)

CCI

Page 17 of 20

Strictly Confidential. © 2023, PRA Health Sciences. All rights reserved.

- Subjects reporting at least 1 clinically significant TEAE (defined by skin irritation score ≥ 2)
- Subjects reporting at least 1 Abilify MyCite treatment related TEAE (Cohort 2 only)
- Subject reported receiving at least 1 TEAE with concomitant or additional therapy
- Subjects with any TEAE leading to death
- Subjects discontinuing the study due to a TEAE
- Subjects discontinuing the study due to a device/patch related TEAE
- Subjects discontinuing the study due to an Abilify MyCite treatment related TEAE

Furthermore, a breakdown of the number and percentage of subjects reporting TEAE, categorized by system organ class (SOC) and preferred term (PT) coded according to the MedDRA dictionary (Version 26.0), will be presented. Note that counting will be by subject not event and subjects are only counted once within each SOC or PT. Therefore, when counting the number of subjects with each event, subjects with multiple events within a particular SOC or PT will be counted under the category of their most severe event within that SOC or PT. The list of TEAE tables is the following:

- TEAEs by SOC and PT
- Clinically significant TEAEs (defined as device/patch related TEAE and skin irritation score ≥ 2) by SOC and PT
- Any TEAE by maximum severity (mild, moderate, severe) by SOC and PT
- Any TEAE related to study device/patch by SOC and PT
- Any TEAE related to Abilify MyCite treatment by SOC and PT (Cohort 2 only)
- Serious TEAEs by SOC and PT
- TEAE leading to death by SOC and PT
- TEAEs leading to study discontinuation by SOC and PT

All AEs recorded on the CRF will be listed with MedDRA SOC and PT. The TEAEs will be marked with a flag within the listing. A footnote will state if no AE occurred after screening and before the subject wore any patches or took any tablet.

Independent listings will be provided with MedDRA SOC and PT for:

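### SAP 10.5 lets an adverse event that began before any patch or tablet count as treatment-emergent because it is serious, with no requirement that anything changed after exposure

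*SAP*

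**What the plan says.** SAP 10.5 builds the TEAE class from two groups. The first is "AEs that occurred on or after the subject wears any patch or takes any tablet from the trial at test day". The second is "the AEs that occurred before the subject wears any patch or takes any tablet and are worsening, serious, related", with death, discontinuation or interruption of the product completing the list. The next sentence makes every remaining recorded event a non-TEAE.

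SAP 12.6 presents the safety analyses for the Safety Analysis Set, which by SAP 9.2.4 contains only subjects who wore a patch or took a trial tablet. SAP 12.6.1 then runs an overall TEAE summary, with rows such as "Subjects reporting at least 1 serious TEAE", and a set of tables by system organ class and preferred term, all on the TEAE flag.

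The protocol collects events before exposure. Protocol 8.7.2 has the investigator assess subjects "from the time the ICF is signed until the end of the trial", and Protocol 5.4 says "All AEs must be reported after subject informed consent has been obtained". Under Protocol 4.1 the testing visit is "conducted either on the same day as Visit 1 or up to 7 days after Visit 1".

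The protocol neither defines nor uses the term TEAE, and SAP 6.1 does not list this definition among the changes from the protocol.

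**The concern.** An event that starts before exposure is normally called treatment-emergent only if something about it changes for the worse once exposure begins. The second group in SAP 10.5 carries no such time condition. Seriousness alone is enough, even if the event was already serious during screening and stayed the same after the patch was placed.

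The secondary objective is to characterise adverse events associated with the device. The serious TEAE row is one of the first that a reader looks at, and in cohorts this small one subject is visible in it. An event that preceded both patch and tablet does not belong in that row unless it changed after exposure.

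**Working it through.** The plan states no figure that depends on this definition, so there is nothing to reproduce. The check is of the wording, with an illustration of size.

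**1. Can a pre-exposure event be recorded?** Yes. Collection starts at consent (Protocol 5.4 and 8.7.2), and the gap from Visit 1 to testing is 0 to 7 days (Protocol 1.3 and 4.1). SAP 12.6.1 itself plans a footnote for the case that no event fell between screening and first exposure.

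**2. Can it reach the TEAE tables?** Yes, if the subject is later exposed and so enters the Safety Analysis Set. Screen failures have no patch applied (Protocol 5.4) and stay out.

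**3. How is each case classified?**

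| Event | SAP 10.5 as written | With a time condition |
|---|---|---|
| Onset on or after first patch or tablet | TEAE | TEAE |
| Earlier onset, severity increases after exposure | TEAE | TEAE |
| Earlier onset, becomes serious after exposure | TEAE | TEAE |
| Earlier onset, leads to study discontinuation after exposure | TEAE | TEAE |
| Earlier onset, already serious before exposure, unchanged after | TEAE, serious | Non-TEAE |
| Earlier onset, not serious, not related, unchanged, no consequence | Non-TEAE | Non-TEAE |

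Only the fifth row differs. No other section of either document adds a condition that would change it.

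**4. What does the relatedness condition add?** Very little. Protocol 8.7.1 calls an event related only if a temporal as well as a causal link to the patch, MIT or Abilify MyCite is reasonably possible. An event that precedes all three and does not change afterwards should not meet that, so such a record would be a misattribution or a data error. Cohort 2 subjects already take aripiprazole, which makes misattribution a little more likely there.

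**5. Size, for illustration.** Inputs: the planned minimum cohort sizes of 24 and 30 (Protocol 9.1, SAP 8.1), all assumed to be in the Safety Analysis Set, with no other serious event. Incidence is k/n, with an exact Clopper-Pearson 95% interval.

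- Cohort 1: 0/24 = 0% (0 to 14.2%) becomes 1/24 = 4.2% (0.1 to 21.1%).
- Cohort 2: 0/30 = 0% (0 to 11.6%) becomes 1/30 = 3.3% (0.1 to 17.2%).
- With two such subjects: 2/24 = 8.3% and 2/30 = 6.7%.

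The documents give no expected number of such events, so these figures show what one or two cases would look like. They do not estimate a bias.

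**The case against.** The strongest reply is that eligibility largely removes the problem. Exclusion 2 in Protocol 5.2.2 bars hospitalization, an emergency room visit, surgery or new medical treatment in the 30 days before testing. It is tied to testing, so it covers the screening week, and Protocol 5.2 allows no exceptions. Most serious events would trip it, and the subject would become a screen failure outside the Safety Analysis Set. This stands, and it is why the practical impact is small. It does not close the gap completely. The schedule of assessments marks eligibility review at Visit 1 only, so an event between the visits could be missed. Also, not every seriousness criterion in Protocol 8.7.1 (permanent impairment, for example) has to involve one of the excluded events.

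A second reply is that the intent is clear. Interruption presupposes exposure, a subject who died before exposure cannot be in the Safety Analysis Set, and worsening suggests a later change. The sponsor may well have meant earlier-onset events with later consequences. That is a fair reading of the purpose, but the text does not state it, and a programmer who follows the sentence will flag the unchanged serious event.

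Some stronger inferences are tempting but not supported:

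- *That the rule attributes pre-exposure events to the device.* It does not. The TEAE flag carries no causality, and SAP 12.6.1 reports device-related and Abilify MyCite-related events in separate rows and tables. An unrelated pre-exposure serious event would not enter those.
- *That every safety output is affected.* Only the TEAE outputs are. Vital signs (SAP 12.6.4) do not use the flag, nor do PDA and latency.
- *That such events are present in the data.* They can be collected. Nothing shows that any occurred, and the window is zero when Visits 1 and 2 fall on the same day.
- *That harm could be hidden.* Compared with a time-anchored definition, the rule can only add events. All adverse events are also listed with the TEAE flag, so a reader could trace one.

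**Conclusion.** The definition is wrong as written and its practical impact is probably small. It classifies an unchanged, pre-exposure serious event in a later-exposed subject as a serious TEAE, and nothing elsewhere in the documents prevents this. The conclusion about the wording rests on the SAP text alone. The judgement of small impact rests on a window of at most 7 days and on Exclusion 2 working as intended. If a case occurs, the affected rows are the overall and serious TEAE counts, where one subject shows as 4.2% in Cohort 1 or 3.3% in Cohort 2 at the planned minimum sizes. No primary result changes. The sentence should be corrected before the flag is programmed, as a low-cost correction.

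**What to change.** Keep the first group as it is. Limit the second group to events with onset before the first patch or tablet that, on or after that time, worsen in severity, become serious, become related, or result in death, discontinuation or interruption. Classify all other pre-exposure events as non-TEAEs and show them in the adverse event listing.

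Do not simply delete every condition other than worsening. That would drop an earlier-onset event that leads to withdrawal after exposure, without a change in severity or seriousness, from the study-discontinuation table in SAP 12.6.1.

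The cost is one SAP sentence and one flag derivation. The derivation needs to know when an event changed. The documents do not show whether the CRF records the date on which severity, seriousness or relatedness changed, so that should be checked, and a rule for an unknown date written into the same section.
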